### 9.2.2. Immediate Reactions

All participants will be observed for immediate reactions for 30 minutes following the first doses of each vaccine, with appropriate medical treatment readily available in case of an anaphylactic reaction following the administration of study vaccine. Immediate reactions will be assessed by a study clinician. All reactions that occur during this time will be recorded. Any immediate reaction which meets the criteria for a serious adverse event must also be documented on an SAE form.

### **9.2.3. Reactogenicity**

Reactogenicity post-vaccination will be assessed from 30 minutes through 14 days following vaccination. All solicited local and systemic signs recorded from 30 minutes through 14 days post vaccination will be considered “related” to study vaccination. The parent will use a structured reactogenicity diary card for recording solicited (pre-listed) and unsolicited reactogenicity. Any reactogenicity continuing beyond 14 days will be documented as an adverse event and followed until resolution.

Any reactogenicity will be managed in accordance with good medical practices by the clinical study site team who will assess and treat or refer the child for medical care as appropriate. If needed to monitor or treat reactogenicity, additional study visits may be conducted. If any acute treatment or medical care is required as a result of harm caused by the study vaccine or study procedure, this care will be provided by the site free of charge. All children reporting reactogenicity will be followed clinically until the condition resolves (returns to baseline) or stabilizes. Conditions likely to be related to the product, whether serious or not, which persist at the end of the trial will be followed up by the study clinician until resolution or stabilization.

The parents of infants enrolled in this study will be instructed to contact the study site staff to report any reactogenicity of concern that their child experiences. In the case of a life-threatening event, they will be instructed to seek immediate emergency care. Where feasible and medically appropriate, parents will be encouraged to seek medical care for the child at the RITM clinic, and to request that the study physician be contacted upon their arrival.

#### **9.2.3.1. Local and Systemic Signs and Symptoms**

All participants will be monitored at home for assessment of local and systemic signs and symptoms occurring from 30 minutes through 14 days following receipt of study vaccines. Parents will be instructed to record reactogenicity on diary cards. Study staff will call parents 2 days following vaccination to check on the participant and ensure the parent is completing the diary card.

Using a standardized data collection instrument, the following local and systemic signs and symptoms will be documented and graded on predefined scales based on functional assessment or magnitude of reaction:

##### **Local reactions (at injection site):**

- Ecchymosis (bruising)
- Erythema (redness)
- Edema (swelling)
- Induration (hardness)
- Pain/tenderness

**Local ecchymosis, erythema, edema, and induration, if present, will be graded as follows:**

- Grade 1:  $\leq 2.5$  cm in diameter.
- Grade 2:  $> 2.5$  cm in diameter with 50% of surface area of extremity segment involved (upper arm or thigh).
- Grade 3:  $\geq 50\%$  surface area of extremity segment involved (upper arm or thigh) OR ulceration OR secondary infection OR phlebitis OR sterile abscess OR drainage.
- Grade 4: potentially life-threatening consequences (e.g., abscess, exfoliative dermatitis, necrosis involving dermis or deeper tissue).

**Injection site pain/tenderness (pain without touching or tenderness when the area is touched), if present, will be graded as follows:**

- Grade 1: pain or tenderness causing no or minimal limitation of use of limb.
- Grade 2: pain or tenderness causing greater than minimal limitation of use of limb.
- Grade 3: pain or tenderness causing inability to perform usual social and functional activities.
- Grade 4: pain or tenderness causing inability to perform basic self-care function OR hospitalization indicated.

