### Secondary Analyses:

1. Non-inferiority for mumps will be demonstrated if the lower limit of the two-sided 95% CI in the difference of the seropositivity rates between the two groups (concurrent administration minus separate administration) 56 days after vaccination is  $>-10\%$ . The 95% CI will be calculated using the Farrington-Manning method.

2. The ratio of anti-measles and anti-rubella GMCs between both treatment groups with 95% CI obtained 56 days after vaccination (ratio of concurrent administration to separate administration) will be calculated using parametric models after log transformation of the concentrations and titers, where applicable.
3. The difference with 95% CI between the anti-measles, anti-mumps, and anti-rubella seroconversion rates 56 days after vaccination for the two groups (concurrent administration minus separate administration) will be calculated using the Farrington-Manning method.
4. The difference with 95% CI between the anti-JE seropositivity rates 28 days after vaccination for the two groups (concurrent administration minus separate administration) will be calculated using the Farrington-Manning method.
5. The ratio of anti-JE GMTs between both treatment groups with 95% CI obtained 28 days after vaccination (ratio of concurrent administration to separate administration) will be calculated using parametric models after log transformation of the titers, where applicable.
6. Safety endpoints will be descriptively summarized in terms of frequency counts and percentages by treatment group and severity, where applicable. Frequency counts and percentages will be provided along with 95% CI, where applicable. The 95% CI will be calculated based on the Exact test.

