### **8.1.3. Specific Clinical Signs and Symptoms of Interest**

During follow-up, all clinical signs and symptoms must be documented. However, the following signs and symptoms and date of onset/occurrence and resolution will be solicited and recorded for all participants from 30 minutes until 14 days post vaccination per section 9.2.3.1. Signs and symptoms to be solicited will be those commonly reported in the large cumulative experience of CD-JEV and MMR in children.

Local Signs/Symptoms at the Injection Site:

- Ecchymosis (bruising)
- Erythema (redness)
- Edema (swelling)
- Induration (hardness)
- Pain/tenderness

General Signs/Symptoms:

- Fever
- Rash
- Cough
- Runny nose
- Change in eating habits
- Diarrhea
- Sleepiness
- Irritability
- Unusual crying
- Vomiting

In addition, a standardized clinical assessment including history and physical examination will be conducted by all clinicians per routine community practice. Evaluation of the above solicited signs/symptoms and unsolicited adverse events will include assessment of severity per Section 9.2.1.

Reported symptoms and clinical signs will be recorded in a daily diary by parent/guardian. Evaluations will be made by qualified study staff on each day of visit to the study clinic (Group 1: Days 0, 14, 28, 56, 84, 98, 112; Group 2: Days 0, 14, 28, 56, 70, 84, 98, 112) and at any time a participant is seen by a clinician.

Parents will be instructed to complete a daily diary of the above Specific Clinical Signs and Symptoms of Interest to the best of their ability. Parents will be instructed to contact a study clinician in the event of illness that may require urgent care to facilitate a rapid assessment of danger signs and assist in arranging transportation by the study to the health center or local hospital, as required. While the event may or may not be attributable to the study vaccines, study staff will follow the ethical imperative of

assisting ill participants once aware of severe illness. After referral, it will be the responsibility of a study clinician to assess and document all signs and symptoms.

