### **9.2. Methods and Timing for Assessing, Recording, and Analyzing Safety Parameters**

#### **9.2.1. Adverse Events**

An adverse event is defined as any untoward medical occurrence in a patient or clinical investigation participant administered a pharmaceutical product, which does not necessarily have a causal relationship with this treatment. An AE can therefore be any unfavorable and unintended sign (including an abnormal laboratory finding), symptom, or disease temporally associated with the use of a medicinal product, whether or not considered related to the medicinal product. The occurrence of an AE may come to the attention of study personnel during study visits and interviews of a study participant presenting for medical care.

Information to be collected on adverse events includes event description, date of onset, clinician's assessment of severity, relationship to study product (assessed only by those with the training and authority to make a diagnosis), and date of resolution/stabilization of the event.

Any medical condition that was present at the time that the patient was enrolled should not be reported as an AE. However, if it deteriorates during the study safety recording periods, it should be recorded as an AE.

AEs should be graded for severity and relationship to vaccine.

**Severity of Event:** Any AE which is not a local and systemic sign or symptom occurring within 14 days of vaccination will be assessed to quantify intensity using the following guidelines:

Grade	Categorization	Definition
Grade 1	Mild	Symptoms causing no or minimal interference with usual social & functional activities with intervention not indicated
Grade 2	Moderate	Symptoms causing greater than minimal interference with usual social & functional activities with intervention indicated.
Grade 3	Severe	Symptoms causing inability to perform usual social & functional activities with intervention or hospitalization indicated.
Grade 4	Potentially life-threatening	Symptoms causing inability to perform basic self-care functions with intervention indicated to prevent permanent impairment, persistent disability, or death.

*\*Intervention defined as medical, surgical, or other procedures recommended or provided by a healthcare professional for the treatment of an adverse event.*

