**Fever if present will be recorded and graded as follows (axillary temperature):**

- Grade 1:  $37.5^{\circ}\text{C}$  to  $37.9^{\circ}\text{C}$
- Grade 2:  $38.0^{\circ}\text{C}$  to  $38.4^{\circ}\text{C}$
- Grade 3:  $38.5^{\circ}\text{C}$  to  $40.0^{\circ}\text{C}$
- Grade 4:  $> 40.0^{\circ}\text{C}$

**Rash, cough, runny nose, change in eating habits, diarrhea, sleepiness, irritability, unusual crying, vomiting, and any other unsolicited reaction occurring from 30 minutes through 14 days post vaccination will be graded as follows:**

- Grade 1: symptoms causing no or minimal interference with usual social and functional activities.
- Grade 2: symptoms causing greater than minimal interference with usual social and functional activities.
- Grade 3: symptoms causing inability to perform usual social and functional activities with intervention or hospitalization indicated.
- Grade 4: symptoms causing inability to perform basic self-care functions OR medical or operative intervention indicated to prevent permanent impairment, persistent disability, or death.

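### Does the Grade 2 line for local skin reactions in Protocol 9.2.3.1 leave a band of reactions without a grade?

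*Protocol*

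**What the plan says.** Protocol 9.2.3.1 says that solicited signs are "documented and graded on predefined scales based on functional assessment or magnitude of reaction", using a standardized data collection instrument and citing an external grading table. For ecchymosis, erythema, edema and induration it then prints four grades:

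- Grade 1: up to and including 2.5 cm in diameter.
- Grade 2: more than 2.5 "cm in diameter with 50% of surface area of extremity segment involved (upper arm or thigh").
- Grade 3: a threshold of at least 50%, followed by the words "surface area of extremity segment involved (upper arm or thigh) OR ulceration OR secondary infection OR phlebitis OR sterile abscess OR drainage".
- The last step, Grade 4, is for reactions that could threaten life.

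Pain/tenderness, fever and the remaining systemic signs have their own scales in the same section.

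Protocol 8.1.3 says that the solicited signs are "solicited and recorded for all participants from 30 minutes until 14 days post vaccination per section 9.2.3.1". For severity it points elsewhere: "Evaluation of the above solicited signs/symptoms and unsolicited adverse events will include assessment of severity per Section 9.2.1". The scale in Protocol 9.2.1 opens by limiting itself: "Any AE which is not a local and systemic sign or symptom occurring within 14 days of vaccination will be assessed".

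On analysis, the Protocol Summary (Secondary Analyses, item 6) says: "Safety endpoints will be descriptively summarized in terms of frequency counts and percentages by treatment group and severity, where applicable". SAP 7.2 tabulates each local and systemic reaction by severity within study group and lists reactions by participant. The SAP does not restate the grades.

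**The concern.** The Grade 2 line gives 50% as a value and not as a limit. A literal reader would conclude that Grade 2 means exactly half of the limb segment, which Grade 3 already includes. The whole range between 2.5 cm and half of the thigh would then have no grade.

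No other printed scale fills the gap. The general scale in 9.2.1 excludes local signs in the first 14 days. The functional scale at the end of 9.2.3.1 covers named systemic symptoms and unsolicited reactions. The severity cross-reference in 8.1.3 leads to the section that excludes these signs.

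What would be at stake is the severity breakdown of four of the five solicited local signs, in an open-label trial where safety is a secondary objective and the grader knows the arm. If graders handled the middle band differently, the Grade 2 counts and the number of ungraded reactions could differ between groups for reasons unrelated to the vaccines.

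**Working it through.** The plan states no figure on this point, so there is none to reproduce. The check is to apply the printed rule to test points and see what each receives.

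**Inputs (Protocol 9.2.3.1).** Let d be the diameter in cm and a the percentage of the segment involved, with no complication present. Grade 1 applies if d ≤ 2.5. Grade 3 applies if a ≥ 50. Grade 2 requires d > 2.5 together with one of three conditions on a: a = 50 (the literal text), a < 50, or a ≤ 50.

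**Result.** The (d, a) pairs are illustrative assumptions, not data.

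| d, a | a = 50 (literal) | a < 50 | a ≤ 50 |
|---|---|---|---|
| 1 cm, 2% | 1 | 1 | 1 |
| 2.5 cm, 5% | 1 | 1 | 1 |
| 2.6 cm, 6% | none | 2 | 2 |
| 4 cm, 15% | none | 2 | 2 |
| 6 cm, 30% | none | 2 | 2 |
| 8 cm, 49.9% | none | 2 | 2 |
| 9 cm, 50% | 2 and 3 | 3 | 2 and 3 |
| 10 cm, 60% | 3 | 3 | 3 |

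The literal gap is therefore real, and it is exactly the region d > 2.5 with a < 50. The two non-literal readings agree everywhere except at the single value a = 50, which the Grade 3 line expressly claims with its own sign.

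**Is the literal reading tenable?** It would make Grade 2 one point on a continuous scale, and a point already inside Grade 3. Grade 2 would then never be the only grade assigned. In an ordered list where Grade 1 stops at 2.5 cm, Grade 2 starts just above 2.5 cm and Grade 3 starts at 50%, the only reading that gives Grade 2 content is the range between. The other numeric scale in the section ("Fever if present will be recorded and graded as follows (axillary temperature") runs without gaps: at 0.1 °C steps from 37.5 to 42.0 there are (42.0 − 37.5)/0.1 + 1 = 46 readings, and each falls in exactly one grade.

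**Could the sign have been lost in conversion?** The other signs in the same list survived, as did less-than signs elsewhere in the Protocol. In the SAP text, however, single signs are damaged. The age formula in SAP 5.1 shows a greater-or-equal sign where a multiplication belongs. The duration formula in SAP 7.2 lacks the minus sign that the parallel formula in SAP 5.3 has. Loss of the sign is neither shown nor excluded.

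**Reach.** Solicited signs: 5 local + 10 systemic = 15, of which 4 use this line. Diary periods per child: 2 in Group 1 (Days 0 and 84) and 3 in Group 2 (Days 0, 56 and 84). Within those, only uncomplicated reactions in the middle band are touched, and only in the severity columns and the listing.

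**The case for a change.** The best case for a correction is that the protocol promises predefined scales and then prints one whose middle step must be inferred. The inference has a loose end: putting in a less-or-equal sign closes the gap but still gives two grades at exactly 50%. Assessment is unblinded, so any judgement is made with knowledge of the arm. The external table and the instrument might settle the matter, but neither can be seen here. The repair would cost one line.

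What stands is that the printed line is defective and that no other visible text supplies the sign. What does not stand is that the outcome is open. Across the middle band every workable reading gives Grade 2, so knowledge of the arm has nothing to act on. The only residual ambiguity is a single boundary value, and the Grade 3 line already includes it.

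Three related points add little:

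- **Severity cross-reference in 8.1.3.** It is incomplete, but the same section already sends these signs to 9.2.3.1, and 9.2.1 expressly excludes them. A reader reaches the right scale by either route.
- **Missing severity.** SAP 3.3.1 words its separate category for adverse events. The Protocol classes solicited reactions as adverse events (Protocol Summary, secondary objective 6b; Protocol 3.2.2 item 6; Protocol 9.1), so an ungraded reaction is already provided for.
- **Safety Monitoring Committee.** Protocol 9.5.2 does not say that its summaries carry grades, so an effect there would be speculation.

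**Conclusion.** This is a clerical slip of one character, possibly only in the converted text, and the plan needs no change. Graders and analysts will place uncomplicated reactions above 2.5 cm and below 50% in Grade 2, because the scale allows no other workable reading. A corrected line would produce the same tables.

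At most, the Grade 2 column for four local signs is involved. The any-occurrence proportions and their exact confidence intervals, pain/tenderness and systemic grades, SAE handling and all immunogenicity results, including both co-primary tests, are the same either way.

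This rests on two assumptions: that staff read the four grades as an ordered scale, and that the diary card and case report form, which are not in the documents, do not carry a conflicting scale. How many children would fall in the band cannot be estimated from the documents, but the conclusion does not depend on that number, since the grade they would receive is not in doubt.

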**Systemic reactions:**

General Signs/Symptoms:

- Fever
- Rash
- Cough
- Runny nose
- Change in eating habits
- Diarrhea
- Sleepiness
- Irritability
- Unusual crying
- Vomiting

**Fever if present will be recorded and graded as follows (axillary temperature):**

- Grade 1:  $37.5^{\circ}\text{C}$  to  $37.9^{\circ}\text{C}$
- Grade 2:  $38.0^{\circ}\text{C}$  to  $38.4^{\circ}\text{C}$
- Grade 3:  $38.5^{\circ}\text{C}$  to  $40.0^{\circ}\text{C}$
- Grade 4:  $> 40.0^{\circ}\text{C}$

**Rash, cough, runny nose, change in eating habits, diarrhea, sleepiness, irritability, unusual crying, vomiting, and any other unsolicited reaction occurring from 30 minutes through 14 days post vaccination will be graded as follows:**

- Grade 1: symptoms causing no or minimal interference with usual social and functional activities.
- Grade 2: symptoms causing greater than minimal interference with usual social and functional activities.
- Grade 3: symptoms causing inability to perform usual social and functional activities with intervention or hospitalization indicated.
- Grade 4: symptoms causing inability to perform basic self-care functions OR medical or operative intervention indicated to prevent permanent impairment, persistent disability, or death.

#### **9.2.4. Serious Adverse Events**

An SAE is defined as an AE that meets one of the following conditions:

- Death.
- Life threatening (participant at immediate risk of death) (*The term “life-threatening” in the definition of “serious” refers to an event in which the patient was at risk of death at the time of the event; it does not refer to an event which hypothetically might have caused death if it were more severe*).
- Requires inpatient hospitalization or prolongation of existing hospitalization.
- Results in a persistent or significant disability or incapacity.
- Important medical events that may not result in death, be life threatening, or require hospitalization may be considered SAEs when, based upon appropriate medical judgment, they may jeopardize the participant and may require medical or surgical intervention to prevent one of the outcomes listed in this definition. Medical and scientific judgment should be exercised in deciding whether reporting is appropriate.

All SAEs occurring at any time during the study must be reviewed and evaluated by a study clinician (SAE relationship to study vaccine must be evaluated as outlined in Section 9.2.1) and recorded on an SAE form and reported (as specified in Section 9.3). All SAEs should be followed until satisfactory resolution or until the study clinician deems the event to be chronic or the patient to be stable.

### **9.3. Reporting Procedures**

#### **9.3.1. Serious Adverse Events**

All SAEs occurring at any time during the study must be reported, even if the investigator considers that the SAE is not related to treatment. The study clinician will complete a Serious Adverse Event Form and send it to the medical monitor with copy to the Sponsor and CRO within 24 hours of site awareness, as outlined in a reporting SOP.

### **9.3.2. Regulatory Reporting**

Collected SAEs will be reported to responsible ethical review committees according to requested timelines. Collected local and systemic reactions and adverse events not meeting the criteria of an SAE will be summarized at the end of the study, and a summary report will be sent to responsible ethical review committees and CDIBP.

## **9.4. Type and Duration of Follow-up of Participants after Adverse Events**

Serious adverse events occurring throughout the study will be recorded. Adverse events likely to be related to the product, whether serious or not, which persist at the end of the trial will be followed up by the study clinician until resolution. The study clinician will document the date of final disappearance of the adverse event on a data clarification form. However, any AE not resolved at the time of data lock will be classified as “unresolved” for data cleaning and locking purposes.

## **9.5. Safety Oversight**

Additional safety oversight will be conducted by a Safety Monitoring Committee (SMC). The SMC will operate under rules of an SMC-approved charter that will be finalized at the organizing meeting of the SMC (first meeting). PATH will draft this charter, and the SMC will approve it, after any modification by the SMC. The draft charter will embody the elements of the following sections.

### **9.5.1. SMC Roles and Responsibilities**

An SMC will be constituted for independent safety review of this trial. The SMC will review individual and cumulative participant safety data when making recommendations regarding the safe continuation of the study. SMC members will not participate in the study, nor will they fall under the direct supervision of any investigator participating in the study.

PATH will, prior to any review of data, confirm that no conflicts of interest exist with any SMC member. Interests that might create a potential conflict of interest should be disclosed to PATH prior to any review of safety data. PATH will determine if the relationship is in conflict or gives the appearance of a conflict such that the individual should not serve on the SMC. PATH will determine how to handle such potential conflicts. PATH might dismiss an SMC member in the event of an unmanageable potential conflict.

